An open-label vasopressor test will be performed increasing MAP up to 80–85 mmHg by using progressive incremental doses of NE in patients with previous history of chronic hypertension and persistently abnormal CRT or unfulfilled lactate goals accompanied by a fluid unresponsive state. Parameters will be reassessed 1 h after in

the PPTR and 2 h after in the LTR. If after the vasopressor test, CRT improves, and lactate goals are achieved in PPTR and LTR, respectively, NE will be titrated to maintain this new MAP goal throughout the study period. If goals are not achieved despite increasing MAP, or NE dose surpasses 0.8 mcg/kg/min or adverse effects are observed (heart rate (HR) > 140 ppm, arrhythmias or evident cardiac ischemia), NE dose will be reduced to the level before the vasopressor test, and the protocol will move to the next step.

Inodilator test

An open-label test of dobutamine at fixed 5 mcg/kg/min or milrinone at fixed 0.25 mcg/kg/min doses (at discretion of the attending physician) will be started in patients with persistent abnormal CRT or non-achieved lactate goals, and negative FR status. CRT and lactate goals will be rechecked such as in the vasopressor test. If such resuscitation goals are not reached, drugs will be discontinued and no further action will be taken during the study period, except for rechecking FR every hour and restart fluid challenges if the patient gets again FR+. Dobutamine or milrinone doses will be maintained throughout the study period in those favorably responding to the open-label inodilators test. As a safety measure,

inodilators will be stopped if HR increases >15%, or arrhythmias, ischemia or hypotension develop.

Management of peripheral perfusion-targeted resuscitation

As a safety measure, if signs of inadequate macrohemodynamics persist such as HR > 120 BPM or unstable MAP with increases in vasopressors during the last hour, resuscitation will be continued even if CRT is normal.

After CRT normalization at any step, it will be reassessed hourly during the study period. If at any point it turns abnormal again, the resuscitation sequence will be restarted (Fig. 2)

Management of lactate-targeted resuscitation

Lactate will be assessed every 2 h during the 8-h study period. If after achieving lactate goals, it becomes again abnormal or the decrease rate slow down under 20%/2 h at any of the following controls, the resuscitation sequence will be restarted (Fig. 2).

Safety measures

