The protocol can be stopped at any moment for safety considerations during the 8-h study period if the attending intensivist considers that the patient has developed unexpected and severe complications or evolves into refractory shock, conditions that under his judgment require liberalization of management. This action has to be reported on the case report form (CRF), and the patient will be followed up with major outcomes, and included in the intention-to-treat (ITT) analysis. Specific safety measures for fluid administration, vasopressor test and inodilator use are specified above.

Suspected unexpected serious adverse reactions (SUSAR)

Any adverse event that occurs in a clinical trial subject, which is assessed by the study investigator as being unexpected, serious and as having a reasonable possibility of a causal relationship with the study procedure will be reported. Reports of these reactions are subject to expedited submission to health authorities. SUSAR's will be analyzed by both the SCC and the data safety monitoring committee (DSMC).

Blinding

Since the intervention will be administered to critically ill patients (mostly sedated), blinding of these patients is not necessary. Because this is a non-pharmacological intervention, blinding of the medical team is not feasible.

Data collection and management

Study follow-up and the variables that will be collected are described below.

Baseline

Demographics, comorbidities, acute physiology and chronic health evaluation (APACHE) II [31], sepsis source and treatment

pre-ICU resuscitation and fluid balance

Sequential Organ Failure Assessment (SOFA) [26] + and Acute Kidney Injury Network (AKI) criteria [32]

Hemodynamics: HR, SBP, diastolic blood pressure (DBP), MAP, CVP, FR status, intraabdominal pressure (IAP), NE levels, diuresis.

Perfusion: lactate, central venous O₂ saturation (ScvO₂), central venous arterial pCO₂ gradient (P(cv-a)CO₂), Hb, central venous and arterial blood gases, CRT, mottling score.

Evolution

SOFA and AKI criteria at 8, 24, 48 and 72 h

Hemodynamics hourly up to 8 h

Fluid administration and balance at 8, 24, 48 and 72 h

Complete perfusion assessment when the targeted parameter is normalized and then at 8, 24, 48 and 72 h

Register of vasoactive drugs and dobutamine/milrinone use

Register of MV and RRT

Source control re-analysis at 4 h

Rescue therapies: HVHF, vasopressin, epinephrine, steroids, others.

Echocardiography at least once during the study period

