In patients predicted to be fluid-responsive, the first resuscitation step will be to administer a fluid bolus (500 ml of crystalloids) every 30 min until normalizing capillary refill time in the PPTR group. In the LTR group, fluid boluses will be stopped if at 2h lactate is normalized or has decreased >20%, or previously if after any of the fluid boluses, central venous pressure has increased ≥ 5 mmHg or the patients has become fluid unresponsive.

An open-label vasopressor test will be performed increasing mean arterial pressure up to 80-85 mmHg by using progressive incremental doses of norepinephrine in patients with previous history of chronic hypertension (as defined by previous use of anti-hypertensive medications and medical history) and persistently abnormal capillary refill time or unfulfilled lactate goals accompanied by a fluid unresponsive state. Parameters will be reassessed one hour after in the PPTR and two hours after in the LTR. If after the vasopressor test, capillary refill time improves, and lactate goals are achieved in PPTR and LTR respectively, norepinephrine will be titrated to maintain this new mean arterial pressures goal throughout the study period. If goals are not achieved despite increasing mean arterial pressure, or norepinephrine dose is higher than 0.8 mcg/kg/min or adverse effects are observed (heart rate > 140 ppm, arrhythmias, or evident cardiac ischemia), norepinephrine dose will be reduced to the level before the vasopressor test, and the protocol will move to the next step.

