An open-label test of dobutamine at fixed 5 mcg/kg/min or milrinone at fixed 0.25 mcg/kg/min doses (at discretion of the attending physician) will be started in non-hypertensive patients with persistent abnormal capillary refill time or non-achieved lactate goals, and negative fluid-responsive status. Similarly, this open-label test of inodilators will be performed in hypertensive patients with persistently abnormal resuscitation parameters and a failed vasopressor test. Capillary refill time and lactate goals will be rechecked such as in the vasopressor test. If such resuscitation goals are not reached, drugs will be discontinued and no further action will be taken during the study period, except for rechecking fluid responsiveness every hour and restart fluid challenges if the patient gets again fluid responsive. Dobutamine or milrinone doses will be maintained throughout the study period in those favorably responding to the open-label inodilators test, i.e., those showing an improvement in capillary refill time or lactate goals (according to the group assigned). As a safety measure, inodilators will be stopped if heart rate increases >15%, or arrhythmias, ischemia or hypotension develop.

The protocol can be stopped at any moment for safety considerations during the 8h-study period if the attending intensivist considers that the patient has developed unexpected and severe complications or evolves into refractory shock, conditions that under his judgment requires liberalization of management.

SAMPLE SIZE

Mortality in patients with increased lactate levels in circulatory dysfunction has been shown to exceed 40%.¹¹ In addition, several studies have shown that abnormal peripheral perfusion is associated with a mortality exceeding 40% as well, whereas a normal CRT in

the early phase of septic shock has been associated with a less than 10% mortality.^{12,13} We anticipate a mortality within 28-days of 45% in the LTR group of our trial.

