We will estimate the effect on mechanical ventilation-free days, renal replacement therapy-free days and vasopressors-free days within 28 days with generalized linear models using the distribution that better fits the data (possibly truncated Poisson distribution). Effects on organ dysfunction at 72 hours (measured by SOFA) will be calculated with generalized linear models with the distribution that better fits the data with adjustment for the baseline SOFA. Effect on other continuous outcomes, such as ICU or hospital length of stay, amount or resuscitation fluids, fluid balance, will also be calculated with generalized linear models with the distribution that better fits the data (normal, gamma, inverse Gaussian, or other), without adjustment for covariates.

Subgroup analyses

We will use Cox proportional hazards adjusted for baseline covariates (same as main analysis) to assess interactions between treatment effect and the following prespecified subgroups: a) Patients with lactate > 4.0 mmol/L versus equal or lower than 4 mmol/L; b) Patients without a confirmed source of infection (as this could increase the translation of

the study to other critically ill) versus those with confirmed source of infection; c) Patients with APACHE II lower versus equal or higher than 25; d) Patients with SOFA score lower versus equal or higher than 10; e) Patients with a more than 10% difference in lactate levels between the very first one measured and the baseline when starting the study.

Sensitivity analysis

We will assess the effect of PPTR compared to LTR on 28-day mortality using a frailty Cox model with site as random effect and adjustment for the same baseline co-variables as in the main analysis (APACHE II score, SOFA score, lactate level, CRT and source of infection).

Harms

Our primary, secondary and tertiary outcomes are intended to reflect potential harms resulting from the PPTR versus LTR approach for managing septic shocks.

Missing data

Primary outcome (28-day mortality) will be treated as time to event outcome and reported as Cox proportional hazard models, patients with loss of follow up will be censored in the last contact. We will use multiple imputation methods to assess treatment effect on the primary outcome if there are cases without no follow-up information at all. As a sensitivity analysis, we will also assess the effect on the primary outcome using complete case data.

Statistical software

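### No by-arm comparison is specified for the named drug-test stopping events, safety stops of the 8-hour protocol, or suspected unexpected serious reactions

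*SAP*

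**What the plan says.** The whole SAP Harms section is one sentence, on the management of septic shock: "Our primary, secondary and tertiary outcomes are intended to reflect potential harms resulting from the PPTR versus LTR approach". The outcomes it refers to are listed under Outcome definitions: mortality at 28 and 90 days and in hospital, days free of ventilation, renal replacement and vasopressors, SOFA at 72 hours, lengths of stay, resuscitation fluids, fluid balance, intra-abdominal hypertension and use of renal replacement.

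Both documents also name events that end a drug test:

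- **Vasopressor test.** Norepinephrine returns to its earlier level if, among other reasons, "adverse effects are observed (heart rate > 140 ppm, arrhythmias, or evident cardiac ischemia" (SAP, Study interventions; the protocol's Vasopressor test section says the same).
- **Inodilator test.** "inodilators will be stopped if heart rate increases >15%, or arrhythmias, ischemia or hypotension develop" (SAP, Study interventions; likewise the protocol's Inodilator test section).

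The protocol's Safety measures section lets the attending intensivist stop the 8-hour protocol for safety and adds "This action has to be reported on the case report form (CRF". Its SUSAR section requires these reactions to be reported and says "SUSAR's will be analyzed by both the SCC and the data safety monitoring committee (DSMC".

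**The concern.** The SAP chooses which outcomes stand for harm, so this is a stated decision and not an omission. The difficulty is that the chosen outcomes do not include the acute events that the trial's own drug-test rules treat as reasons to stop.

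Exposure to those tests may differ by arm. After a vasopressor or inodilator test, the goal is re-checked at 1 hour in the peripheral-perfusion arm and at 2 hours in the lactate arm, and the rule for ending fluid boluses differs as well. The number of tests and the time on each drug can therefore differ between arms. Mortality or SOFA at 72 hours would not show whether one strategy brought more arrhythmia or ischaemia within the first 8 hours.

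What is at stake is the completeness of the safety report. A paper that followed the plan could present equal or lower mortality and give no count by arm of tests stopped for adverse effects, of protocols stopped for safety, or of SUSARs.

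**Working it through.** **1. Items against provisions.** I read every outcome list, analysis section and mock table in the SAP, and the safety and data-collection sections of the protocol.

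| Item | Nearest provision | By-arm event comparison specified? |
|---|---|---|
| Arrhythmia, ischaemia | None | No |
| Hypotension, tachycardia | Mock table 2: mean heart rate and blood pressures by arm, 2 to 72 h, with P values | No; means at fixed times, not episodes |
| Drug test stopped for an adverse effect | Mock table 2: norepinephrine dose and use by arm; protocol register of vasoactive drugs and inodilators | No |
| Safety stop of the 8-hour protocol | Entered on the case report form; may fall under non-adherence counts (SAP, Adherence and protocol deviations) | No split by arm or by safety reason stated |
| SUSARs | Review by the coordinating centre and the monitoring committee | No |

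**2. What is recorded.** The protocol's data-collection list includes use of vasoactive drugs and of dobutamine or milrinone. It has no item for arrhythmia or ischaemia, for episodes of hypotension, or for why a test was stopped. Only the safety stop of the whole protocol is expressly sent to the case report form. Arrhythmia, ischaemia and hypotension are named but not defined. Numbers are given only for heart rate (above 140, or a rise above 15%) and for the norepinephrine limit.

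**3. Size.** The documents give no figure for harms, so there is none to reproduce. To check the formula, I applied it to the plan's own power statement (SAP, Sample size: 210 per group, 45% versus 30%, two-sided 5%):

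power = Φ{ [|p1 − p2| − 1.96 √(2p̄(1−p̄)/n)] / √[p1(1−p1)/n + p2(1−p2)/n] }

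= Φ{ (0.150 − 0.0926) / 0.0467 } = Φ(1.23) = 89.1%, which agrees with the stated approximately 90%.

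*Zero-event bound.* If no event is seen in n patients, the one-sided 95% upper limit is 1 − 0.05^(1/n), or roughly 3/n.
- n = 210 (all randomised, one arm): 3/210 = 1.4%; exact 1.4%.
- n = 60 (assumed number exposed): 3/60 = 5%; exact 4.9%.

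*Example difference, 3% versus 8% (assumed rates).* At 210 per arm, p̄ = 0.055 and power = Φ{ (0.050 − 1.96 × 0.02225) / 0.02211 } = Φ(0.29) = 61%. With Fisher's exact test, which the SAP names for most binary secondary and tertiary outcomes, it is about 55%. With an assumed 60 per arm, Fisher power is about 9%.

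*Precision at 210 per arm.* The half-width of the 95% CI for a risk difference is 1.96 √(2p(1−p)/210) when both arms have rate p. All rates are assumed.

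| Assumed rate | CI half-width (points) | Rate in the other arm detectable with 80% power |
|---|---|---|
| 2% | 2.7 | 8.0% |
| 5% | 4.2 | 12.8% |
| 10% | 5.7 | 19.7% |
| 15% | 6.8 | 26.1% |
| 20% | 7.7 | 32.0% |

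These figures use all randomised patients. The vasopressor test is confined to fluid-unresponsive patients with chronic hypertension and unmet goals. The inodilator test is confined to fluid-unresponsive patients with unmet goals, after a failed vasopressor test where one applies. Among test recipients, precision will be worse by an amount the documents do not allow one to state.

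**The case against.** The strongest reply is that the chosen outcomes do measure the harm that motivates the trial. Both documents stress over-resuscitation, and the SAP compares fluids, fluid balance, intra-abdominal hypertension, renal replacement and SOFA by arm. Mock table 2 adds mean heart rate, blood pressures and norepinephrine. Serious consequences of an arrhythmia or ischaemic event could also reach mortality, SOFA or vasopressor-free days. This stands, so a reader should not infer that the plan has only efficacy outcomes or no view of harm. One qualification is that intra-abdominal pressure was measured only on clinical suspicion, and the treating team was not blinded.

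A second reply is that the mock tables are those intended for the main paper and do not rule out further safety reporting. Non-adherence counts may include protocol stops, the committee reviews SUSARs, and the flow diagram is not shown in the text reviewed. This also stands. A reader might conclude that these events will never be compared, but the documents support only the statement that no comparison is specified. Committee review does not replace a comparison in the report, however, and the SAP records that the committee set no statistical stopping guidance for safety in advance.

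A third reply concerns data. If reasons for stopping were not captured, recovering undefined events from charts in an unblinded trial, after 388 patients had already been recruited when the protocol paper was submitted, would invite ascertainment bias. This is correct and limits the fix.

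**Conclusion.** The point holds as a gap in pre-specified safety reporting. The outcomes that stand for harm cover over-resuscitation, but no by-arm comparison is specified for the events named as reasons to stop a drug test, for safety stops of the 8-hour protocol, or for SUSARs. It is worth correcting because the correction is cheap. It does not affect the primary analysis.

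The size is unknown, because event rates and numbers exposed are not given. Two stronger statements should be avoided. One is that a difference such as 3% versus 8% would plainly be seen: power is about 61% even with all 210 per arm. The other is that zero events would exclude a rate above 1.4% for test-related harms. That bound applies only to all-randomised denominators, and would be 5% if 60 per arm were exposed, which is an assumption. The added table would inform on common events and be descriptive for rare ones. Nor do the documents show that every item is already recorded: safety stops and drug use are, but reasons for stopping a test are not listed.

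**What to change.** Replace the Harms sentence with a by-arm safety table, pre-specified before database lock and built from data already on the case report form:

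- vasopressor and inodilator use, and tests started where this can be identified;
- safety stops of the 8-hour protocol, with the reason where recorded;
- SUSARs;
- where captured, tests stopped, with the reason (heart-rate limit, arrhythmia, ischaemia, hypotension).

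Report counts, percentages and risk differences with 95% CI. Use two denominators: all randomised patients, which preserves the randomised comparison, and patients who received each test, which describes risk given exposure but is not a randomised comparison. State which items were not captured, and do not collect undefined events retrospectively. Keep the existing outcomes as the assessment of over-resuscitation and say so.

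The cost is one descriptive table and some data queries, with low precision for rare events. No new patients, procedures or changes to clinical rules are needed.

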Hemodynamic and perfusion-related variables		
Heart rate, mean (SD), bpm	xx.x (xx.x)	xx.x (xx.x)
Mean arterial pressure, mean (SD), mmHg	xx.x (xx.x)	xx.x (xx.x)
Norepinephrine dose, mean (SD), mcg/kg/min	x.xx (x.xx)	x.xx (x.xx)
Central venous pressure, mean (SD), mmHg	xx.x (xx.x)	xx.x (xx.x)
Serum lactate, mean (SD), mmol/L	x.xx (x.xx)	x.xx (x.xx)
Central venous oxygen saturation, mean (SD), %	xx.x (xx.x)	xx.x (xx.x)
Venous-arterial pCO2 gradient, mean (SD), mmHg	xx.x (xx.x)	xx.x (xx.x)
Capillary refilling time, median (IQR), sec	x (x to x)	x (x to x)
Mottling score, median (IQR)	x (x to x)	x (x to x)
Initial management data		
Time from matching entry criteria to randomization, mean (SD), min.	xx (xx)	xx (xx)
Intravenous fluid loading before randomization, mean (SD), mL	xxxx (xxxx)	xxxx (xxxx)
Time from diagnosis of septic shock to first antibiotics, mean (SD), min.	xxx (xxx)	xxx (xxx)

Abbreviations: SD, standard deviation; IQR, interquartile range; bpm, beats per minute; SOFA, Sequential Organ Failure Assessment; APACHE, Acute physiology and chronic health evaluation.

Table 2. Evolution of Hemodynamic and Perfusion Variables from Baseline to 72 hours in the peripheral perfusion-targeted resuscitation (PPTR) and lactate-targeted resuscitation (LTR) groups

Variable	Group	Basal	2h	4h	8h	24h	48h	72h
Number of patients	PPTR	xxx	xxx	xxx	xxx	xxx	xxx	xxx
	LTR	xxx	xxx	xxx	xxx	xxx	xxx	xxx
Heart rate, mean, bpm	PPTR	xxx	xxx	xxx	xxx	xxx	xxx	xxx
	LTR	xxx	xxx	xxx	xxx	xxx	xxx	xxx
	P-value	-	x.xx	x.xx	x.xx	x.xx	x.xx	x.xx
Systolic blood pressure, mean, mmHg	PPTR	xxx	xxx	xxx	xxx	xxx	xxx	xxx
	LTR	xxx	xxx	xxx	xxx	xxx	xxx	xxx
	P-value	-	x.xx	x.xx	x.xx	x.xx	x.xx	x.xx
Diastolic blood pressure, mean, mmHg	PPTR	xx	xx	xx	xx	xx	xx	xx
	LTR	xx	xx	xx	xx	xx	xx	xx
	P-value	-	x.xx	x.xx	x.xx	x.xx	x.xx	x.xx
Mean arterial pressure, mean, mmHg	PPTR	xx	xx	xx	xx	xx	xx	xx
	LTR	xx	xx	xx	xx	xx	xx	xx
	P-value	-	x.xx	x.xx	x.xx	x.xx	x.xx	x.xx
Norepinephrine dose, mean, mcg/Kg/min	PPTR	x.xx	x.xx	x.xx	x.xx	x.xx	x.xx	x.xx
	LTR	x.xx	x.xx	x.xx	x.xx	x.xx	x.xx	x.xx
	P-value	-	x.xx	x.xx	x.xx	x.xx	x.xx	x.xx
Norepinephrine use, no. (%)	PPTR	xx (xx.x)	xx (xx.x)	xx (xx.x)	xx (xx.x)	xx (xx.x)	xx (xx.x)	xx (xx.x)
	LTR	xx (xx.x)	xx (xx.x)	xx (xx.x)	xx (xx.x)	xx (xx.x)	xx (xx.x)	xx (xx.x)
	P-value	-	x.xx	x.xx	x.xx	x.xx	x.xx	x.xx

Diuresis, mean, total mL in previous period	PPTR	-	xxx	xxx	xxx	xxx	xxx	xxx
	LTR	-	xxx	xxx	xxx	xxx	xxx	xxx
	P-value	-	x.xx	x.xx	x.xx	x.xx	x.xx	x.xx
Lactate, mean, mmol/L	PPTR	x.xx	x.xx	x.xx	x.xx	x.xx	x.xx	x.xx
	LTR	x.xx	x.xx	x.xx	x.xx	x.xx	x.xx	x.xx
	P-value	-	x.xx	x.xx	x.xx	x.xx	x.xx	x.xx
Capillary refill time, median, sec	PPTR	x	x	x	x	x	x	x
	LTR	x	x	x	x	x	x	x
	P-value	-	x.xx	x.xx	x.xx	x.xx	x.xx	x.xx
Central venous oxygen saturation, mean, %	PPTR	xx	-	-	xx	xx	xx	xx
	LTR	xx	-	-	xx	xx	xx	xx
	P-value	-	-	-	x.xx	x.xx	x.xx	x.xx
Delta PaCO ₂ , mean, mmHg	PPTR	xx.x	-	-	xx.x	xx.x	xx.x	xx.x
	LTR	xx.x	-	-	xx.x	xx.x	xx.x	xx.x
	P-value	-	-	-	x.xx	x.xx	x.xx	x.xx
Mottling score, median	PPTR	x	-	-	x	x	x	x
	LTR	x	-	-	x	x	x	x
	P-value	-	-	-	x.xx	x.xx	x.xx	x.xx

Abbreviations: Delta PaCO₂, central venous-arterial pCO₂ gradient

Table 3. Outcomes of Patients Treated with Peripheral Perfusion-Targeted Resuscitation versus Lactate-Targeted Resuscitation

Outcome	Peripheral perfusion-targeted resuscitation (n=xxx)	Lactate-targeted resuscitation (n=xxx)	Type of effect estimate	Effect estimate (95% CI)	P Value
Primary Outcome					
Death within 28 days, no. (n%)	xx (xx.x)	xx (xx.x)	Hazard ratio	x.xx (x.xx to x.xx)	x.xx
Secondary Outcomes					
Death within 90 days, no. (n%)	xx (xx.x)	xx (xx.x)	Hazard ratio	x.xx (x.xx to x.xx)	x.xx
Mechanical ventilation-free days within 28 days, mean (SD)	xx.x	xx.x	Mean difference	x.x (x.x)	x.xx
Renal replacement therapy-free days within 28 days, mean (SD)	xx.x	xx.x	Mean difference	x.x (x.x)	x.xx
Vasopressor-free days within 28 days, mean (SD)	xx.x	xx.x	Mean difference	x.x (x.x)	x.xx
SOFA, mean (SD)					
SOFA at 8h	x.x	x.x	Mean difference	x.x (x.x)	x.xx
SOFA at 24h	x.x	x.x	Mean difference	x.x (x.x)	x.xx
SOFA at 48h	x.x	x.x	Mean difference	x.x (x.x)	x.xx
SOFA at 72h	x.x	x.x	Mean difference	x.x (x.x)	x.xx
ICU length of stay, mean (SD), d	x.x	x.x	Mean difference	x.x (x.x)	x.xx
Hospital length of stay, mean (SD), d	x.x	x.x	Mean difference	x.x (x.x)	x.xx
Tertiary Outcomes					
Amount Resuscitation fluids, mean (SD), mL					
At 8 h	xxxx (xxxx)	xxxx (xxxx)	Mean difference	xxx (xxx to xxx)	x.xx
At 24 h	xxxx (xxxx)	xxxx (xxxx)	Mean difference	xxx (xxx to xxx)	x.xx
Total fluid balance, mean (SD), mL					
At 8 h	xxxx (xxxx)	xxxx (xxxx)	Mean difference	xxx (xxx to xxx)	x.xx
At 24 h	xxxx (xxxx)	xxxx (xxxx)	Mean difference	xxx (xxx to xxx)	x.xx
At 72 h	xxxx (xxxx)	xxxx (xxxx)	Mean difference	xxx (xxx to xxx)	x.xx

Intra-abdominal hypertension, no. (%)	xx (x.x)	xx (x.x)	Risk difference	x.x (x.x to x.x)	x.xx
Use of renal replacement therapy, no. (%)	xx (x.x)	xx (x.x)	Risk difference	x.x (x.x to x.x)	x.xx
In-hospital mortality, no. (%)	xxx (xx.x)	xxx (xx.x)	Risk difference	x.x (x.x to x.x)	x.xx

Abbreviations: SOFA, Sequential Organ Failure Assessment.
